The protocol, informed consent form(s), recruitment materials, and all participant materials will be submitted to the Institutional Review Board (IRB) for review and approval. Approval of both the protocol and the consent form must be obtained before any participant is enrolled. Any amendment to the protocol will require review and approval by the IRB before the changes are implemented to the study. In addition, all changes to the consent form will be IRB-approved; a determination will be made regarding whether a new consent needs to be obtained from participants who provided consent, using a previously approved consent form.

1 PROTOCOL SUMMARY

1.1 SYNOPSIS

Title:	Repurposing a histamine antagonist to benefit patients with pulmonary hypertension (REHAB-PH)
Study Description:	
Pulmonary arterial hypertension (PAH) is one of many conditions that put stress and strain on the right side of the heart. This stress and strain can cause right heart failure. Although there are medications to treat PAH, there are currently no medications that act directly on the heart to improve right heart function. This is different than left heart failure where one of the cornerstones of treatment is medication targeted at the heart to improve left heart function.
 
Famotidine is a well-tolerated, over-the-counter, and inexpensive medication. Preliminary results suggest that famotidine may help the right heart to adapt and strengthen when stressed instead of fail; however, these results are suggestive and not definitive. A randomized controlled trial is required to evaluate the possibility that famotidine can impact right heart function.

Objectives:	
Primary Objective: To determine whether famotidine increases six-minute walk distance at 24 weeks in men and women with pulmonary arterial hypertension.
 
Secondary Objectives:

- To determine whether famotidine reduces BNP at 24 weeks
- To determine whether famotidine improves New York Heart Association (NYHA) functional class at 24 weeks
- To determine whether famotidine improves right ventricular morphology at 24 weeks including improved right ventricular diameter and TAPSE
- To determine whether famotidine improves health related quality of life as estimated by the emPHasis-10 score
- To determine whether famotidine decreases the need to escalate PAH focused care (increased diuretics, escalating doses of pulmonary vasodilators, and/or adding an additional pulmonary vasodilator)
- To explore changes in invasive hemodynamics with famotidine
- To explore changes in gas exchange, maximal oxygen uptake, metabolism, and myocardial reserve with famotidine

Sub-study Objectives:

Exercise sub-study:

- To determine whether famotidine increases maximal oxygen uptake in individuals with pulmonary arterial hypertension at 24 weeks
- To explore changes in other metrics of the exercise response (oxygen uptake, V_e/V_{CO_2} ratio, total achieved wattage) with famotidine relative to placebo over 24 weeks.
- In a “right heart targeted therapy” trial, to explore the relationship between markers of the exercise response and other standard markers of treatment response including BNP, New York Heart Association functional class, quality of life, and need to escalate PAH-specific therapy.

Right heart catheterization sub-study

- To determine whether famotidine increases stroke volume index at 24 weeks
- To explore whether famotidine is associated with differences in wedge pressure, right atrial pressure, and/or pulmonary vascular resistance at 24 weeks
- In a “right heart targeted therapy” trial, to explore the relationship between markers of the exercise response and other standard markers of treatment response including BNP, New York Heart Association functional class, quality of life, and need to escalate PAH-specific therapy.

[figure not shown]
Endpoints:

Primary endpoint: The difference between treatment groups in 6-minute walk distance (6MWD) at 24 weeks.

Secondary endpoint: The difference between treatment groups in BNP, NYHA functional class, TAPSE, right ventricular basal diameter, emPHasis-10 score, and number of participants with an escalation of routine clinical treatments for PAH for each visit.

Study Population:	Approximately 80 participants, male or female, age 18 to 80 with WHO Group 1 Pulmonary Arterial Hypertension and NYHA Functional Class II, III, or IV at screening.
Phase:	II
Description of Sites/Facilities Enrolling Participants:	All potential subjects for the REHAB-PH Trial will be recruited from the University of Washington Pulmonary Vascular Disease Program.
Description of Study Intervention:	Famotidine, 20 mg daily, per oral
Study Duration:	60 months
Participant Duration:	Participants will be evaluated and participate over 24 ± 1 weeks.

1.2 SCHEMA

All patients in the pulmonary vascular disease clinic are pre-screened using the electronic medical record.

Those interested in participation and eligible will be consented at their baseline visit. For most participants in the main study, all study assessments will occur during one study visit; however, sub-study participants and occasional main study participants may have study assessments on two or more different days. If this occurs then randomization will occur following the last baseline study assessment. Individuals who appear to violate inclusion or exclusion criteria as a result of baseline assessments before randomization will be considered screen failures and not randomized.

Study drug will be dispensed on the day of the last study assessment and will be started the day following the last baseline assessment. All baseline assessments must be completed over the 14 days before study drug is started. Study drug start date will be considered Day 0.

1.3 SCHEDULE OF ACTIVITIES (SOA)

	Baseline	Randomization	Phone Visit Week 4	Week 12	Week 24
Visit #	1		Non-visit PH	2	3
Day #	-14 to -1	-1	0 28 ± 7	84 ± 7	168 ± 7
Inclusion/Exclusion Criteria					
	X				
Informed Consent					
	X				
History and physical exam					
Demographics					
	X				
Medical history					
	X				
Symptom assessment					
	X			X	X
Concomitant medications					
	X			X	X
Vital Signs & Weight					
	X			**X	X
Physical Examination					
	X			**X	X
Safety laboratories					
Laboratory Draw					
	X				X
Comprehensive metabolic panel					
	X				X
Complete blood count					
	X				X
Mass-Spectrometry for H ₂ antagonists					
	X				X
Pregnancy test if premenopausal					
	X				X
Endpoint assessment					
6 minute-walk distance (primary)					
	X			** X	X
echocardiogram					
	X				X
emPHasis-10 score					
	X			X	X
BNP					
	X				X
NYHA functional class					
	X			X	X
Study Procedures					
Dispense study drug					
		X		X	
Start study drug					
			X		
Study drug adherence					
			X	X	X
Study drug compliance					
			X	X	X
Adverse events					
	X		X	X	X
Study Termination					
					X
Sub-study components					
Right heart catheterization (n=20)					
	X				X
Cardiopulmonary Exercise Test (n=10)					
	X				X
Covid testing for exercise test (as required per lab requirement)					
	X				X
Miscellaneous					

Data Safety Monitoring Board	Semi-annually
------------------------------	---------------

As per clinical practice guidelines, patients will be seen every three to six months with blood work and six-minute walk testing. These elements (visit, laboratory draw, comprehensive metabolic panel, complete blood count, BNP, pregnancy test, 6 minute-walk distance, and NYHA functional class) will be collected as part of routine medical care and abstracted from the medical record as research endpoints. The pregnancy test can be performed as either a blood or urine test. A blood-based pregnancy test is preferred; however, if a urine test is used then it must be performed by study personnel and documented in the medical record. Echocardiograms are often part of routine medical care and will be abstracted from the medical record as research endpoints; however, the frequency may be influenced by the study. To avoid any concern about overlap, any echocardiogram occurring more frequently than annually will be considered research. It is anticipated that 1 of the 2 echocardiograms will fit this research definition. Other research elements include mass spectrometry for H₂ antagonists, the emPHasis-10 score, study procedures, and sub-study components.

** These procedures will not be performed if the visit is done remotely.

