7 STUDY INTERVENTION DISCONTINUATION AND PARTICIPANT DISCONTINUATION/WITHDRAWAL

7.1 PARTICIPANT DISCONTINUATION/WITHDRAWAL FROM THE STUDY

Participants are free to withdraw from participation in the study at any time upon request.

An investigator may discontinue or withdraw a participant from the study for the following reasons:

- Pregnancy
- Serious Adverse event(s) related to the trial medication
- Any relevant deterioration in the health of the subject (AEs, vital signs, laboratory parameters).
- Protocol violation
- Subject's inability to stay on the study drug or off other H2 blockers
- Subject withdrew consent

The reason for participant discontinuation or withdrawal from the study will be recorded on the Case Report Form (CRF).

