7.2 LOSS TO FOLLOW-UP

A participant will be considered lost to follow-up if he or she fails to return for a scheduled visit and is unable to be contacted by the study site staff.

The following actions must be taken if a participant fails to return to the clinic for a required study visit:

- The site will attempt to contact the participant and reschedule the missed visit within a week and counsel the participant on the importance of maintaining the assigned visit schedule and ascertain if the participant wishes to and/or should continue in the study.
- Before a participant is deemed lost to follow-up, the investigator or designee will make every effort to regain contact with the participant (where possible, 3 telephone calls and, if necessary, a certified letter to the participant's last known mailing address or local equivalent methods). These contact attempts should be documented in the participant's study file.
- Should the participant continue to be unreachable, he or she will be considered to have withdrawn from the study with a primary reason of lost to follow-up.

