9.4 STATISTICAL ANALYSES

9.4.1 GENERAL APPROACH

Except where otherwise noted, all tests will be two-sided and statistical significance will be determined at the 0.05 level.

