10.1.1.2 CONSENT PROCEDURES AND DOCUMENTATION

Informed consent is a process that is initiated prior to the individual's agreeing to participate in the study and continues throughout the individual's study participation. Consent forms will be Institutional Review Board (IRB)-approved and the participant will be asked to read and review the document. A study team member will explain the research study to the participant and answer any questions that may arise. A verbal explanation will be provided in terms suited to the participant's comprehension of the purposes, procedures, and potential risks of the study and of their rights as research participants. Participants will have the opportunity to carefully review the written consent form and ask questions prior to signing. The participants will be given adequate opportunity to consider all options by allowing subjects to take the consent form home and to contact the study team at a later time if they would like to participate. The participant will sign the informed consent document prior to any procedures being done specifically for the study. Participants must be informed that participation is voluntary and that they may withdraw from the study at any time, without prejudice. A copy of the informed consent document will be given to the participants for their records. The informed consent process will be conducted and documented in the source document (including the date), and the form signed, before the participant undergoes any study-specific procedures. Study-specific procedures (like right heart catheterization) may be scheduled but not performed before consent is obtained. Many of the study endpoints including the six-minute walk distance, BNP, NYHA functional class, and echocardiogram are also part of routine clinical care. As such clinically obtained testing within the specified time window may be used as part of the baseline research assessment. Because these tests are not "study-specific" it is not considered a violation if they are obtained before consent is obtained. The rights and welfare of the participants will be protected by emphasizing to them that the quality of their medical care will not be affected if they decline to participate in this study.

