5.5 Visit Windows

All visits (scheduled, unscheduled or withdrawal) will be mapped to an analysis visit as defined in Table 5-1, where Day 0 is defined as the date of first dose of study treatment. All safety and efficacy analyses will be based on the analysis visit. In cases where a subject has more than one particular analysis visit, the visit with non-missing data closest to the protocolled visit will be selected for analysis.

Table 5-1: Evaluation Intervals for Efficacy Analysis

Scheduled Visit	Protocol-Specified Interval	Interval for Analysis Visit
Baseline	Day –14 to Day –1	Day –14 to Day -1
Week 12	Day 77 to Day 91	Day 0 to Day 125
Week 24	Day 161 to Day 175	Day 126 to Day 175

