6 STATISTICAL METHODS

6.1 Sample Size Justification

The primary endpoint is the change in six-minute walk distance (6MWD). The study was powered to detect a difference of 31.9 meters. A 31.9 meter improvement in 6MWD is well aligned with established thresholds for a minimally important difference in patient reported outcomes (Mathai SC, et al. Am J Respir Crit Care Med, 2012; 186(5):428-433). The 6MWD was chosen because it is a surrogate for patient-centered outcomes and was the primary endpoint in labeling trials for most of the medications used to treat pulmonary arterial hypertension (PAH).

Standard deviation in 6MWD among PAH participants with NYHA functional class II, III, or IV symptoms is 37.6 meters (national Pulmonary Hypertension Association Registry; unpublished data). As shown, the proposed sample size has adequate power (0.96) to detect a minimally important difference in 6MWD even with 10% attrition in the study sample (power, 0.94).

Table 6-1: Power to detect a minimally important difference in 6MWD (31.9 meters)

Alpha	Sample size per group	Power for the total sample size	Sample size per group with ~10% attrition	Power with attrition
0.05	20	0.74	18	0.69
0.05	40	0.96	36	0.94
0.05	60	0.99	54	0.99

The field is appropriately shifting toward larger event driven trials; however, we did not feel a larger event driven trial of famotidine was warranted at this juncture. The current proposal is the first randomized evaluation of this drug and this pathway in individuals with right heart failure and/or PAH and a smaller Phase II trial was felt to be a more appropriate next step.

For the RHC sub-study, the initial sample size was set at 10 participants based on the following power to detect large differences.

Size of difference	SV index (mL/m2)	Total sample size	n per group	power
Large	20	10	5	0.87
Medium-high	15	10	5	0.67
Medium-low	10	10	5	0.36
Small	5	10	5	0.13

For the exercise sub-study, the initial sample size was set at 10 participants based on the following power to detect large differences.

Size of difference	VO2 (mL/min/kg)	Total sample size	n per group	power
Large	8	10	5	0.96
Medium	4	10	5	0.46
Low	2	10	5	0.15

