6.4.1 Primary efficacy analysis

The primary endpoint is the difference between treatment groups in the change of 6-minute walk distance (6MWD) between baseline and 24 weeks. Linear regression will be performed for the FAS with the change in 6MWD between baseline and 24 weeks as outcome and treatment group as the primary predictor of interest, adjusted for baseline 6MWD and baseline NYHA functional class as the stratification variable. The estimate of the treatment effect will be provided with associated 95% confidence interval (CI).

Missing 6MWD at 24 weeks will be imputed as follows. Subjects known to be dead before the 24 week assessment will have zero imputed for their 24 week 6MWD. Missing 24 week 6MWD for subjects who are alive will be imputed using multiple imputation. The imputation model will have prognostic variables as the predictor variables. Prognostic variables will include age, gender, and etiology of pulmonary hypertension, baseline six minute walk test distance, baseline right ventricular diameter, and baseline BNP. The multiple imputation will use Markov Chain Monte Carlo (MCMC), which assumes that the variables in the imputation model have a joint multivariate normal distribution (MVN). The number of imputations to be performed will be 100. One hundred is selected because it is not too large that it requires heavy computations

and is not too small (such that the Monte Carlo error is still small enough at around 0.1 times the standard deviation). The “proc mi” procedure in SAS will be used to impute the missing observations.

PAH etiology in the analysis will be as follows:

- Idiopathic
- Familial
- Congenital Heart Disease
- Collagen Vascular Disease
- Toxin
- Portopulmonary Hypertension

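### For participants who leave the study, nothing continues abstraction of routine clinic walks, and the SAP's early-withdrawal visit is in neither schedule

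*Protocol*

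**What the plan says.** Protocol 1.3 lists 6MWD, NYHA class, BNP and laboratory tests among the elements that "will be collected as part of routine medical care and abstracted from the medical record as research endpoints". It puts routine visits at every three to six months; the note under SAP Table 9-1 says every three months. Protocol 10.1.1.2 gives explicit permission to use clinic tests, but for baseline: "As such clinically obtained testing within the specified time window may be used as part of the baseline research assessment".

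On participants who leave:

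- Protocol 7.1 lists reasons for withdrawal and has the reason entered on the case report form. It names no exit assessment and no later data collection.
- Protocol 7.2 requires documented attempts to regain contact. If these fail: "Should the participant continue to be unreachable, he or she will be considered to have withdrawn from the study". No chart check is named.
- SAP 5.4 follows participants who stop study drug early through Week 24. It does not address leaving the study.
- SAP 5.2 defines an early withdrawal visit, and SAP 5.5 states: "All visits (scheduled, unscheduled or withdrawal) will be mapped to an analysis visit". Protocol 1.3 and SAP Table 9-1 contain no such visit; study termination is marked only at Week 24.
- SAP 6.4.1 states: "Missing 24 week 6MWD for subjects who are alive will be imputed using multiple imputation". The listed predictors are age, gender, etiology, and baseline walk, right ventricular diameter and BNP.

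**The concern.** All participants come from one clinic (Protocol 5.5), and the walk is a test that this clinic does anyway. Someone who gives up study visits but stays a patient there may have a walk in the same chart, dated inside the Week 24 analysis interval. The plan gives no instruction to look for it before imputing.

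Protocol 7.1 counts deteriorating health among the reasons for withdrawal, so some leavers may have done worse than their baseline predicts. Imputation from baseline variables assumes that, given those variables, leavers walk like those who stayed. If that is wrong and the arms lose different numbers, the treatment estimate shifts. BNP, echocardiogram and safety laboratories are also scheduled after baseline only at Week 24, so early leavers have none of them for the secondary endpoints or the laboratory shift tables.

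**Working it through.** **1. The plan's own power.** Inputs: two-sided 0.05 (Protocol 9.4.1); difference 31.9 m, SD 37.6 m, and 40 per arm, or 36 after about 10% attrition (SAP 6.1). Two-sample t test, noncentrality = 31.9 / (37.6 × √(2/n)), df = 2n − 2.

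| n per arm | Noncentrality | Power | SAP Table 6-1 |
|---|---|---|---|
| 40 | 3.79 | 0.963 | 0.96 |
| 36 | 3.60 | 0.944 | 0.94 |

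The plan's figures reproduce. Recovering all 8 lost walks is worth 0.963 − 0.944 = 0.019, about 2 points. Precision is not the issue.

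**2. How many walks the chart might hold.** SAP Table 5-1 accepts Day 126 to 175 as Week 24, which is 50 days. Assume visits at a fixed interval with random timing.

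- Every 3 months: 50/91 = 55%; × 8 = 4.4 walks.
- Every 6 months: 50/183 = 27%; × 8 = 2.2 walks.

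Random timing is a strong assumption. A visit 182.6 days after a baseline on Day −14 to −1 falls at about Day 169 to 182, on both sides of the Day 175 limit. Protocol 1.2 has most main-study participants complete baseline in one visit and start drug the next day. For them, a visit exactly six months on is near Day 182 and just misses.

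**3. Bias.** Let D be the metres by which leavers truly fall short of their imputed walk, and pF and pP the shares missing on famotidine and placebo. The estimate shifts by (pF − pP) × D.

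- Equal shares and equal D: 0 m.
- A 10-point difference, for example 6 of 40 against 2 of 40 (15% and 5%): 0.10 × 30 = 3 m; 0.10 × 50 = 5 m; 0.10 × 100 = 10 m.
- Against the 31.9 m target: 3/31.9 = 9% to 10/31.9 = 31%.

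The shift favours famotidine if more leave that arm and goes against it if more leave placebo. The split and D are assumed; the documents give neither.

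**4. Whether a recovered walk would be used.** SAP 5.5 maps unscheduled and withdrawal visits to analysis visits. SAP 5.2 says unscheduled results are listed but kept out of tables and graphs. As written, a clinic walk in the interval could be treated either way. A walk before Day 126 maps to Week 12, which is not among the imputation predictors, so it would not inform the primary analysis.

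**5. Who counts as a leaver.** Protocol 7.1 gives inability to stay on study drug as a reason for withdrawal from the study. SAP 5.4 follows people who stop drug to Week 24. The same person could fall under either rule.

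**The case against.** A reader might infer that follow-up ends for anyone who stops treatment, and that measured walks are being discarded in favour of imputed ones. The documents support neither. SAP 5.4 continues follow-up after early drug discontinuation, and Protocol 5.5 has staff stress follow-up despite non-adherence. Nothing says that a measured walk is to be discarded: Protocol 1.3 sets no end to abstraction at exit, SAP 5.5 maps all visits, and SAP 6.4.1 imputes only what is missing. A walk that is abstracted within Day 126 to 175 would not be missing.

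Other points also count. Protocol 7.2 asks for rescheduling, calls and a certified letter, so loss to follow-up is actively resisted. SAP 6.4.1.1 adds a worst-case analysis (zero for every missing walk) and a complete-case analysis, and known deaths already receive zero. The 10% attrition is an allowance in a power table, not a forecast. Chart access after withdrawal of consent depends on consent wording that is not available here.

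These arguments narrow the point to people who leave the study itself, and make any loss of real data conditional on a clinic walk in the interval and permission to read it. They do not close the gap. The written permission to use clinic tests covers baseline, no passage directs abstraction after exit, and SAP 5.2 could bar the result. The sensitivity analyses show how far the result depends on the missing-data assumption; they do not replace any of it with measurement.

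**Conclusion.** The point holds for participants who leave the study, as distinct from those who only stop drug. For them the plan gives no clear route by which a measured clinic walk takes precedence over imputation, and the SAP's withdrawal visit exists in neither schedule.

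The size is modest and mostly assumed. With 8 leavers and randomly timed visits, about 2 to 4 walks could be recovered, and fewer if visits cluster just after Day 175. The bias at stake is 0 m under equal loss with equal error, and about 3 to 10 m under a 10-point difference with a 30 to 100 m shortfall. Abstraction would remove only part of this. It is a worthwhile, inexpensive improvement, not a flaw that invalidates the primary analysis.

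**What to change.** 1. In Protocol 1.3, 7.1, 7.2 and the consent form, state that leaving study visits does not end abstraction of routine-care 6MWD, NYHA class, BNP, laboratory tests, echocardiogram and PAH medicines through Day 175, unless the participant refuses chart access. In SAP 6.4.1, impute only if no walk exists in the Week 24 interval.
2. Reconcile SAP 5.2 with SAP 5.5 on unscheduled results, so that such a walk enters the analysis.
3. Reconcile Protocol 7.1 with SAP 5.4 on participants who cannot stay on drug, and align Protocol 1.3 and SAP Table 9-1 with the withdrawal visit that the SAP names.
4. Add Week 12 6MWD to the imputation model, so that walks before Day 126 inform the primary analysis. It will be absent where the Week 12 visit was remote; the planned MCMC imputation can handle an incomplete predictor.

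Cost: a protocol and consent amendment, a SAP revision, chart abstraction for a few people, and an exit assessment for those who agree to one. Some recovered walks will be weeks from Day 168, which Table 5-1 already accepts.
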